8 SAFETY ASSESSMENTS

The safety and tolerability profile of obicetrapib 10 mg + ezetimibe 10 mg FDC therapy, obicetrapib 10 mg as monotherapy, and ezetimibe 10 mg as monotherapy will be assessed by clinical laboratory assessments (chemistry, hematology, and coagulation), vital signs, physical examinations, and the incidence of AEs and events of special interest (ESIs).

8.1 Adverse Events

An AE is defined as any untoward medical occurrence in a clinical investigation participant administered a pharmaceutical product, which does not necessarily have a causal relationship with this treatment. An AE can therefore be any unfavorable and/or unintended sign (including a clinically significant abnormal laboratory finding), symptom, or disease temporally associated with the use of an investigational medicinal product (IMP), whether or not related to the IMP. All AEs, including observed or volunteered problems, complaints, or symptoms, are to be recorded on the appropriate eCRF.

AEs, which include clinical laboratory assessment variables, will be monitored and documented from the time of first dose of study treatment until completion of Visit 5 (Day 112). Participants should be instructed to report any AE that they experience to the Investigator, whether or not they think the event is due to a study drug. Beginning at the date of the first dose of study treatment, Investigators should make an assessment for AEs at each visit and record the event on the appropriate AE eCRF.

Wherever possible, a specific disease or syndrome rather than individual associated signs and symptoms should be identified by the Investigator and recorded on the eCRF. However, if an observed or reported sign or symptom is not considered a component of a specific disease or syndrome by the Investigator, it should be recorded as a separate AE on the eCRF. Additionally, the condition that led to a medical or surgical procedure (eg, surgery, endoscopy, tooth extraction, or transfusion) should be recorded as an AE, not the procedure itself.

Any medical condition already present at the date of the first dose of study treatment should be recorded as medical history and not be reported as an AE unless the medical condition or signs or symptoms present at baseline changes in severity, frequency, or seriousness at any time during the study. In this case, it should be reported as an AE.

Clinically significant abnormal laboratory or other examination findings (eg, ECG) that are detected during the study or are present at the date of the first dose of study treatment and significantly worsen during the study should be reported as AEs, as described below. The Investigator will exercise his or her medical and scientific judgment in deciding whether an abnormal laboratory finding or other abnormal assessment is clinically significant. Clinically significant abnormal laboratory values occurring during the study will be followed until repeat tests return to normal, stabilize, or are no longer clinically significant. Abnormal test results that are determined to be an error should not be reported as an AE. Laboratory abnormalities or other abnormal clinical findings (eg, ECG abnormalities) should be reported as an AE if any of the following are applicable:

- If an intervention is required as a result of the abnormality;
- If action taken with a study drug is required as a result of the abnormality; or

• Based on the clinical judgment of the Investigator.

8.1.1 Adverse Reaction

All noxious and unintended responses to a medicinal product related to any dose should be considered an adverse drug reaction. "Responses" to a medicinal product means that a causal relationship between a medicinal product and an AE is at least a reasonable possibility, ie, the relationship cannot be ruled out.

8.1.2 Unexpected Adverse Drug Reaction

An Unexpected Adverse Drug Reaction is defined as an adverse reaction, the nature or severity of which is not consistent with the applicable product information.

For the obicetrapib 10 mg + ezetimibe 10 mg FDC, the reference safety information is included in Section 6 of the Investigator's Brochure currently in force. The reference safety information will be reviewed annually by the Sponsor and the periodicity of the review will be harmonized with the reporting period of the Development Safety Update Report, where possible.

For ezetimibe, the reference safety information is included in the Summary of Product Characteristics.

8.1.3 Assessment of Adverse Events by the Investigator

The Investigator will assess the severity (intensity) of each AE as mild, moderate, or severe, and will also categorize each AE as to its potential relationship to the study drugs using the categories of yes or no.

Assessment of severity

Mild – An event that is easily tolerated and generally not interfering with normal daily activities.

Moderate – An event that is sufficiently discomforting to interfere with normal daily activities.

Severe – An event that is incapacitating with inability to work or perform normal daily activities.

Causality assessment

The relationship of an AE to the administration of the study drugs is to be assessed according to the following definitions:

No (unrelated, not related, unlikely to be related) – The time course between the administration of study drugs and the occurrence or worsening of the AE is not consistent with a causal relationship and another cause (concomitant drugs, therapies, complications, etc) is suspected.

Yes (possibly, probably, or definitely related) – The time course between the administration of study drugs and the occurrence or worsening of the AE is consistent with a causal relationship and no other cause (concomitant drugs, therapies, complications, etc) can be identified.

The definition implies a reasonable possibility of a causal relationship between the event and the study drugs. This means that there are facts (evidence) or arguments to suggest a causal relationship.

The following factors should also be considered:

• The temporal sequence from a study drug administration-

The event should occur after a study drug is given. The length of time from study drug exposure to event should be evaluated in the clinical context of the event.

• Underlying, concomitant, intercurrent diseases-

Each report should be evaluated in the context of the natural history and course of the disease being treated and any other disease the participant may have.

Concomitant drug-

The other drugs the participant is taking or the treatment the participant receives should be examined to determine whether any of them might be recognized to cause the event in question.

• Known response pattern for this class of study drug-

Clinical and/or preclinical data displayed in the Investigator's Brochure may indicate whether a particular response is likely to be a class effect.

• Exposure to physical and/or mental stresses-

The exposure to stress might induce adverse changes in the recipient and provide a logical and better explanation for the event.

• The pharmacology and PK of the study drugs-

The known pharmacologic properties (absorption, distribution, metabolism, and excretion) of the study drugs should be considered.

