3.5.1 Adverse Events (AEs)

AEs will be categorized by primary system organ class and preferred term as coded using the current MedDRA version category designation.

An overview of treatment-emergent AEs (TEAEs) will be provided including counts and percentages of participants with the following:

- Any TEAEs (overall and by maximum severity)
- Any TEAEs (non-serious)
- Any study drug related TEAEs (overall and by maximum severity)
- Any TEAEs leading to discontinuation of study drug
- Any drug related TEAEs leading to discontinuation of study drug
- Any treatment-emergent serious AEs (TESAEs)
- Any study drug related TESAEs
- Any TEAEs leading to death.

The TEAEs described above will be summarized separately by system organ class and preferred term. The non-serious TEAEs occurring in more than 2% of participants in any treatment group and preferred term will be summarized.

Listings will be presented specifically for TEAEs, TESAEs, TEAEs leading to discontinuation of study drug, and TEAEs leading to death.

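### The Yes/No causality definitions in Protocol section 8.1.3 leave two kinds of event uncategorised and are narrower than section 8.1.1, so drug-related events may be classified inconsistently

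*Protocol*

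**What the plan says.** Protocol section 8.1.3 tells the investigator to "categorize each AE as to its potential relationship to the study drugs using the categories of yes or no", and then defines each category by two conditions joined by *and*.

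- **No** applies when the time course "is not consistent with a causal relationship and another cause (concomitant drugs, therapies, complications, etc) is suspected".
- **Yes**, whose label begins "Yes (possibly, probably, or definitely related", applies when the time course "is consistent with a causal relationship and no other cause (concomitant drugs, therapies, complications, etc) can be identified".

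A sentence below the definitions says they imply a reasonable possibility of a causal link, and adds: "This means that there are facts (evidence) or arguments to suggest a causal relationship". A list of further factors follows, among them concomitant disease and concomitant drugs.

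Section 8.1.1 sets the test for an adverse drug reaction separately: a causal relationship "is at least a reasonable possibility, ie, the relationship cannot be ruled out".

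SAP section 3.5.1 uses the investigator's call in its overview, which includes "Any study drug related TEAEs (overall and by maximum severity"), drug-related TEAEs leading to discontinuation, and drug-related TESAEs.

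**The concern.** A two-way classification needs definitions that between them cover every event. Here each category needs two conditions at once, and the two definitions are opposite on both conditions, so mixed cases have no home. The mixed case with plausible timing and a competing explanation is a natural one in this trial. Participants are on maximally tolerated lipid-modifying therapy, and eligibility covers ASCVD, type 2 diabetes and treated hypertension. The protocol names concomitant drugs, therapies and complications as possible other causes.

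Such an event can satisfy section 8.1.1 and yet fail the Yes definition in section 8.1.3. Two investigators among the approximately 60 sites could classify the same event differently, each with support in the text. At stake are the counts of drug-related events, and the reporting and unblinding steps that depend on relatedness.

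**Working it through.** The plan states no figure on this point to reproduce. The check sets the texts side by side.

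**Step 1. Apply both definitions to every combination (section 8.1.3).**

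| Time course | Other cause | Meets Yes? | Meets No? | Category |
|---|---|---|---|---|
| Consistent | None identified | Yes | No | Yes |
| Consistent | Identified | No | No | Neither |
| Not consistent | Suspected | No | Yes | No |
| Not consistent | None | No | No | Neither |

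Two of the four rows have no category, and the text gives no default for them.

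**Step 2. Compare the standards.**

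- The Yes label reaches down to possibly related events. The Yes definition demands that no other cause be identifiable. An event with a competing cause can fit the label and fail the definition.
- The explanatory sentence asks only for facts or arguments suggesting a link. The definition asks for more.
- The factor list treats other drugs and diseases as things to weigh. The definition makes an identified alternative disqualifying.
- Section 8.1.1 asks whether the relationship can be ruled out. It does not require other causes to be absent.

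The second row of the table is therefore uncategorised under section 8.1.3, but is an adverse reaction under section 8.1.1 whenever the relationship cannot be ruled out.

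**Step 3. Trace where the call is used.**

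- SAP 3.5.1: the three drug-related entries listed above.
- SAP 3.5.2: new-onset diabetes and macular degeneration, summarised by relationship to study drug.
- Protocol 5.4: the sponsor or designee unblinds SAE reports judged unexpected and related.
- Protocol 8.3: all SAEs are reported up to 30 days after the last dose; after that, only those the investigator considers related.

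The 30-day limit bites mainly after early discontinuation. With a last dose on Day 84 the window runs to 84 + 30 = Day 114, beyond the nominal Day 112 visit. With a last dose on Day 28 it ends at 28 + 30 = Day 58, leaving 112 − 58 = 54 days of planned follow-up in which mandatory SAE reporting depends on the relatedness call. Adverse events are still recorded on the eCRF through Visit 5 (section 8.1).

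**Step 4. Scale, for illustration only.** Let q be the share of time-consistent events with another identifiable cause, and f the share of those that investigators mark No. Neither is in the documents; both are assumed. The count marked related, as a share of all time-consistent events, is 1 − q × f.

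| q | f = 0 | f = 0.5 | f = 1 |
|---|---|---|---|
| 10% | 100% | 95% | 90% |
| 30% | 100% | 85% | 70% |
| 50% | 100% | 75% | 50% |
| 70% | 100% | 65% | 30% |

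For example, q = 0.30 and f = 0.5 give 1 − 0.15 = 0.85. The reference is every time-consistent event, not the true number of related ones. The result runs from no loss to a large one, depending wholly on how investigators resolve a gap that the text leaves open.

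**The case against.** The strongest reply is that the wording is loose but the intent is recoverable. The Yes label, the reasonable-possibility sentence and section 8.1.1 all point towards Yes for an event with plausible timing and a competing cause. The No definition excludes that event as firmly as the Yes definition does, because its timing is consistent. An investigator who works from the labels alone has a place for every event. This stands as far as direction is concerned: the text does not send the uncategorised events to No. It does not close the gap, because section 8.1.3 says that relatedness is to be assessed by the definitions.

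The consequences are also limited. All SAEs up to 30 days after the last dose are reported within 24 hours whatever their causality. Expedited reporting is the sponsor's or designee's task (section 8.5), and an unexpected reaction is defined through the adverse-reaction concept, which carries the broader test (sections 8.1.1 and 8.1.2). Events of special interest are monitored whether or not they were reported as adverse events, and liver enzymes, bilirubin and CK are summarised from laboratory values. Safety is descriptive, and the same definitions apply in all arms of a double-blind trial. All of this stands and narrows the point.

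A reader might infer that liver and muscle events cannot be marked related in most participants because most take a statin. The documents do not support that. The protocol aims for about 70% on high-intensity statins and allows no more than about 10% completely statin intolerant. It also says that statins are not required, so a figure of 90% on a statin is an inference. In any case, statin use does not measure how often another cause is identified: the definition asks for a cause that can be identified, not one that is conceivable, and background statin doses must have been stable for at least 8 weeks before Screening.

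**Conclusion.** The definitions are not exhaustive, and the Yes text conflicts with its own label, with the sentence below it and with section 8.1.1. Both statements follow from the wording alone and need no assumption about event rates.

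The supported consequence is a risk of inconsistent classification between sites. Under-counting of drug-related events is possible, and the strict Yes wording makes it the likelier direction, but its size cannot be estimated from the documents. A reader might conclude that related events will be under-counted, or that related SAEs will be kept out of expedited review. Neither is shown: the text assigns no default box, and causality does not restrict SAE reporting within the 30-day window.

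The effect is confined to the four uses in Step 3 of the working. All-cause AE and SAE counts, laboratory-based special-interest summaries and the efficacy analyses do not use this call. The wording should be corrected, but the trial's main conclusions do not depend on it.

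**What to change.** Replace the two definitions in Protocol section 8.1.3 with a pair that is exhaustive and mutually exclusive and that matches section 8.1.1:

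- **Yes:** there is a reasonable possibility that study drug contributed to the event, even if another cause is also possible.
- **No:** all other events.

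Time course and alternative causes then belong only in the list of factors to weigh, where the section already places them. Use the same wording in the eCRF completion guidance.

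The cost is a change of protocol and eCRF-guidance text, with no effect on sample size, the efficacy analysis or the SAP table structure. The count of related adverse events may rise in all arms. If events have already been classified under the present text, state before unblinding whether they will be re-assessed, so that the tables do not mix two standards unannounced.

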8.1.4 Events of Special Interest

ESIs will be monitored, regardless of whether these events were reported as AEs. Any events that qualify as an AE or SAE will be reported accordingly (see Sections 8.1, 8.2, and 8.3).

ESIs will include the following hepatic abnormalities, muscle-related abnormalities, new-onset diabetes mellitus (NODM) and/or hyperglycemia, renal abnormalities, changes to antihypertensive medication(s) due to changes in blood pressure, and ophthalmic events (ie, macular degeneration), described as follows:

- AST or ALT > 3 × ULN;
- Total bilirubin >2 × ULN;
- CK >5 × ULN;
- NODM or worsening of glycemic control;

Note: NODM is defined by 1 or more of the following criteria, based upon information from AE, medication, and laboratory data:

- o AE indicating new type 1 or type 2 diabetes;
- o Initiation of anti-diabetes medication with confirmation of the diagnosis of diabetes by blinded external review by experts in diabetology;

- o HbA1c \geq 6.5% (\geq 0.065 hemoglobin fraction); and/or
- Two consecutive values of fasting plasma glucose that are \geq 126 mg/dL (\geq 7.0 mmol/L).

Note: Worsening of glycemic control will be defined as an HbA1c increase from baseline >0.5% (>0.005 hemoglobin fraction) and/or a new concomitant medication or increase in current antidiabetic therapy in a participant with a baseline HbA1c $\ge 6.5\%$ (≥ 0.065 hemoglobin fraction).

- A >25% decrease in eGFR from baseline or an eGFR <15 mL/min/1.73 m², calculated using the Chronic Kidney Disease Epidemiology Collaboration equation, and/or an increase in serum creatinine of ≥0.3 mg/dL (≥26.5 μmol/L) from baseline;
- Changes to antihypertensive medication(s) due to changes in blood pressure in those
 participants receiving antihypertensive medication(s) treatment at baseline, and new
 antihypertensive medication prescriptions for participants not previously treated for
 hypertension; and
- Macular degeneration.

These ESIs will be monitored through review of the AE and laboratory databases.

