5.6.3 Documentation of Prior and Concomitant Medication Use

Any prior lipid-modifying therapies, administered at any time, must be recorded. Any non-lipid-modifying medications administered within 90 days prior to the first dose of study drug must be recorded. All prior and concomitant medications must be documented in the source documents and applicable eCRFs. Concomitant medications will continue to be assessed and recorded at every study visit from the time of informed consent until study participation is complete.

Data from all participants regarding lipid-modifying medications taken throughout the study will be recorded. The number of participants taking a statin or PCSK9-targeted therapy during the study and the number of participants who discontinue background statin therapy, along with the reasons for discontinuation of background statin therapy, will be recorded in the applicable eCRFs.

A participant's maximally tolerated stable statin dose will be determined by the Investigator using his/her medical judgment and available sources, including the participant's self-reported history of lipid-modifying therapy, for at least 8 weeks prior to Screening (Visit 1), and recorded in the applicable eCRFs.

No more than approximately 10% of participants in this study will be completely statin intolerant. For any participant not taking statin therapy due to statin intolerance (as defined in Inclusion Criterion 4), including those participants taking bempedoic acid or fibrate monotherapy, written confirmation will be required of both the participant and the Investigator stating that the participant is statin intolerant, aware of the benefit of statins to reduce the risk of a MACE, and aware that many other patients who are unable to tolerate a statin were actually able to tolerate a different statin or dose. Statin intolerance should be recorded as intolerance to any dose of any statin as historical events attributed to the statin in question, in the source documentation and eCRF as part of the medical history to confirm intolerance to statins.²⁵

Documentation in the eCRF of the reason why a participant is unable to take HIS is required.

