8.1.4.5 Guidelines for monitoring and management of changes to antihypertensive medication(s)

Any changes to antihypertensive medication(s) due to changes in blood pressure in those participants receiving antihypertensive medication(s) treatment at baseline will be assessed by the Investigator, primary care physician, or other appropriate health care provider to assess for etiologies of blood pressure change, to confirm clinical safety of the participant, to assess the need for any AE or SAE reporting, and to arrange for appropriate medical follow-up.

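### Protocol 8.1.4 promises ESI monitoring that does not depend on AE reports, but its monitoring rule names no medication source for medication-defined ESIs, and SAP 3.5.2 counts the antihypertensive ESI only alongside a hypertension AE

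*Protocol*

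**What the plan says.** Protocol 8.1.4 opens with the principle that "ESIs will be monitored, regardless of whether these events were reported as AEs". It then lists seven ESIs and closes with the monitoring rule: "These ESIs will be monitored through review of the AE and laboratory databases".

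Three items on the list rest on medication data:

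- The antihypertensive ESI starts "Changes to antihypertensive medication(s) due to changes in blood pressure in those" treated at baseline, and goes on to new prescriptions in people not previously treated for hypertension.
- One NODM criterion is "Initiation of anti-diabetes medication with confirmation of the diagnosis of diabetes by blinded external review by experts in diabetology".
- One limb of worsening glycaemic control is "a new concomitant medication or increase in current antidiabetic therapy in a participant with a baseline HbA1c" of at least 6.5%.

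The NODM note in the same section says the diagnosis is "based upon information from AE, medication, and laboratory data". Protocol 5.6.3 confirms that the records exist: "Concomitant medications will continue to be assessed and recorded at every study visit".

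The site guidance in Protocol 8.1.4.5 covers one limb of the antihypertensive ESI: "Any changes to antihypertensive medication(s) due to changes in blood pressure in those participants receiving antihypertensive medication(s) treatment at baseline will be assessed". It does not mention new prescriptions in untreated participants.

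SAP 3.5.2 repeats the ESI definitions and then gives a counting rule for the antihypertensive ESI. A change or a new start is attributed to blood pressure when the participant has a post-baseline AE with a preferred term from SAP Appendix B and the medication event falls within 30 days of the start of that AE.

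**The concern.** The opening and closing sentences of 8.1.4 pull against each other. A laboratory value cannot show that an antihypertensive was changed or started. With the two databases named, that ESI comes to light only if a site also files an AE, and the opening sentence says this should not matter. The NODM note shows that its authors knew medication data were needed.

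ESI incidence is part of the stated safety assessment (Protocol Section 8, SAP 2.3.4). A count that needs an AE measures something narrower than the protocol's definition, and readers of the ESI table would not see the difference.

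**Working it through.** The plan gives no figure to reproduce. The check matches each ESI criterion to the data that can reveal it, then compares the protocol definition with the SAP derivation. The inputs are Protocol 8.1, 8.1.4, 8.1.4.5, 5.6.3 and Appendices A and B, and SAP 3.5.2 and Appendix B.

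**Step 1. Criterion against named source.**

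| Criterion in 8.1.4 | Defining data | Covered by the AE and laboratory databases? |
|---|---|---|
| AST/ALT, bilirubin, CK, eGFR/creatinine | Laboratory | Yes |
| Macular degeneration | AE | Yes |
| NODM: AE of diabetes | AE | Yes |
| NODM: HbA1c; two consecutive glucose values | Laboratory | Yes |
| NODM: start of anti-diabetes drug, confirmed externally | Medication | Not directly; laboratory values may find the same person |
| Worsening: HbA1c rise above 0.5% | Laboratory | Yes |
| Worsening: new or increased therapy | Medication | Not directly; an HbA1c rise may find the same person |
| Antihypertensive change or new prescription | Medication | Only if an AE is filed |

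So one of seven ESIs is wholly medication-defined, together with one of four NODM criteria and one of two limbs of worsening control.

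**Step 2. How far the laboratory route covers the glycaemic criteria.** HbA1c is scheduled only at Screening, Day 84 and EOT. Fasting glucose is in the chemistry panel at every visit, but it feeds an NODM criterion and not the worsening definition. A participant whose therapy was increased may, because of that therapy, show no HbA1c rise above 0.5% by Day 84. The medication limb exists for that case. External confirmation of an NODM medication start can begin only after someone has noticed the start. SAP 3.5.2 gives no rule for deriving either criterion from medication records.

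**Step 3. The antihypertensive ESI in the SAP.** SAP 3.5.2 identifies two groups: participants with hypertension in their medical history who were treated at baseline, and participants with no prior diagnosis. Both need an Appendix B AE. Compared with the protocol:

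| Participant | Protocol 8.1.4 | SAP 3.5.2 |
|---|---|---|
| Diagnosed, treated at baseline, medication changed for blood pressure, no AE | ESI | Not counted |
| No diagnosis, untreated, newly prescribed, no AE | ESI | Not counted |
| Diagnosed but never treated, newly prescribed, with or without an AE | ESI | Fits neither group |

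The SAP's final tabulation is split by baseline treatment, so it has a column for the third row. No rule in the SAP attributes that participant's prescription to blood pressure.

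**Step 4. Effect on the count.** Let N be the number of antihypertensive ESIs under the protocol definition and f the share that also meets the SAP's AE condition. Then counted = f × N, with f between 0 and 1. Neither N nor f is in the documents. The AE condition can only lower the count. If f is the same in two arms, the absolute difference is multiplied by f and the risk ratio is unchanged. If f differs between arms, the ratio can move either way.

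**The case against.** Several points on the other side are sound.

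- **The monitoring sentence does not say that these are the sole sources.** The NODM note names medication data, and SAP 3.5.2 repeats it. A reader might infer that medication data are never looked at, or that every medication-defined event goes undetected. The documents do not support that. The records are collected at every visit, the SAP uses them for the antihypertensive ESI, and laboratory values give the glycaemic criteria a partial route.
- **Many cases should become AEs anyway.** Under Protocol 8.1 a baseline condition that changes in severity is an AE, and an abnormal finding that requires an intervention should be reported as one. Investigators assess AEs at each visit, so newly prescribed participants are not outside site review. This narrows the gap but does not close it, because a case that is not reported has no other named route.
- **The AE link is an attribution device.** The definition refers to blood pressure as the cause, and the documents show no reason-for-change field for antihypertensives. An AE within 30 days is a workable and specific proxy, and worth keeping as a secondary summary. As the only rule, it restores the dependence that 8.1.4 rules out.
- **A signal could show elsewhere.** Concomitant medications are summarised by ATC class and arm (SAP 3.3.6), and vital signs by visit and arm (SAP 3.5.4). A reader might infer that an imbalance between arms would be hidden altogether; it need not be. Those outputs do not count ESIs as defined, however.
- **Editing 8.1.4 alone would not change the table.** This is correct. The reported antihypertensive count is set by SAP 3.5.2, so both documents have to change.

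**Conclusion.** The inconsistency is real and of moderate weight. It touches no efficacy endpoint, and safety is summarised without inference, but one stated ESI cannot be ascertained as defined.

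- **Antihypertensive ESI:** events without a qualifying AE are not counted under SAP 3.5.2, and diagnosed but untreated participants who are newly prescribed fall outside both SAP groups.
- **Two glycaemic criteria:** events may be missed when HbA1c and glucose do not reveal them. It would go too far to say that they will be.
- **Site guidance:** 8.1.4.5 covers fewer participants than the ESI it serves.

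The number of events affected cannot be estimated from the documents. For the antihypertensive ESI, the direction (too few) follows from the AE condition alone. No statement about the size of a difference between arms is supported. It might also seem that blood-pressure readings should be added as a monitoring source, but no ESI criterion is a blood-pressure value, so the definitions do not call for it.

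**What to change.** 1. **Protocol 8.1.4, last sentence.** Add the concomitant-medication database to the AE and laboratory databases.
2. **Protocol 8.1.4.5 and 8.1.4.** Reconcile the two so that both cover the same participants: those treated at baseline and those newly prescribed.
3. **SAP 3.5.2, antihypertensive ESI.** Derive it from concomitant-medication records for everyone in the protocol definition, whatever their diagnosis history. Keep the AE-linked version as a secondary summary.
4. **SAP 3.5.2, glycaemic criteria.** Add a derivation of the two medication-based criteria from the same records.

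**Cost.** Medication data are already collected at every visit, so the main work is wording, some programming and some site queries. If the eCRF does not capture the indication or the reason for an antihypertensive change, a field may be needed; the documents do not show one. ESI counts would be somewhat higher and less specific, which is the reason to show the AE-linked version beside them.
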